9.2 SAFETY ENDPOINTS

Assessments for safety include AEs, SMBG, clinical laboratory assessments, physical examination, electrocardiogram (ECG), weight, and vital signs. An independent DMC will meet on a regular basis to review accumulating clinical trial safety data.

Adjudication of all deaths, MACE/other selected CV events (MI, stroke, unstable angina leading to hospitalization, and heart failure leading to hospitalization), selected renal events, bone fracture, and DKA will be performed in a blinded manner by a CEC(s) comprised of experts. Details will be provided in the charter of the CEC(s). Further details are available in [Section 6.4](#).

Two expert committees will review all potential cases of DILIs and cases of amputation in a treatment-blinded manner to evaluate causality.

The following safety endpoints will be assessed:

- Adverse events, AEs leading to discontinuation from the IMP, adverse events of special interest (AESIs), events of special interest (EOSIs), SAEs and deaths
- Hypoglycemia (all, severe, and/or documented symptomatic hypoglycemia)
- Clinical laboratory results (including fasting lipids; see [Section 9.2.1.3](#)), vital signs, and ECG results
- Markers of bone and calcium metabolism
- Markers of intestinal transit and absorption

Observation period of safety endpoints

The observation period of safety data will be divided into 3 segments:

- The pre-treatment period is defined as the time between the date of the informed consent and the first dose of double-blind IMP.
- The on-treatment period (TEAE period) is defined as the time from the first dose of double-blind IMP up to 10 days (1 day for hypoglycemia) after the last dose of double-blind IMP, regardless of the introduction of rescue therapy. The 10-day interval is chosen based on the half-life of the IMP (approximately 5 times the half-life of sotagliflozin) in patients with moderate renal dysfunction.
- The post-treatment period is defined as the time starting 11 days after the last dose of double-blind IMP (after the on-treatment period).

The baseline value for safety endpoints in the safety population is the last available value (or the average of all values for creatinine or eGFR) prior to the first administration of double-blind IMP.

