8.2.2 Rescue therapy

The threshold values are defined as follows, depending on study period:

- FPG >270 mg/dL (15.0 mmol/L) from Randomization up through the scheduled Week 8 Visit
- FPG >240 mg/dL (13.3 mmol/L) after the Week 8 visit up through the scheduled Week 12 Visit
- FPG >200 mg/dL (11.1 mmol/L) after the Week 12 Visit through the end of the 26-week Core Treatment Period
- FPG >170 mg/dL (9.4 mmol/L) or HbA1c \geq 8.0% after the Week 26 Visit through the end of the treatment period

Routine fasting SMBG (see [Section 9.2.1.6](#)) and central laboratory alerts on FPG (and HbA1c at Week 26 and onward) are set up to ensure that glycemic parameter results remain under predefined thresholds.

- If one fasting SMBG value exceeds the specific glycemic limit on one day, the patient checks it again during the two following days. If all the values in three consecutive days exceed the specific limit, the patient should contact the Investigator and a central laboratory FPG measurement (and HbA1c at Week 26 and onward) be performed as soon as possible, preferably within 7 days, to confirm the hyperglycemia.
- Upon receipt of a central laboratory rescue alert, a central laboratory re-test must be completed and confirmed as exceeding the threshold for rescue before rescue therapy is initiated. The re-test confirmation should be performed as soon as possible, but within 7 days of receipt, by unscheduled visit.

In the event that a confirmatory FPG and/or HbA1c exceeds the threshold, the Investigator should ensure that no reasonable explanation exists for insufficient glucose control and in particular that:

- The increased FPG has been tested at a fasting status (ie, no food intake for \geq 8 hours)
- Investigational medicinal product is given at the planned dose
- There is no intercurrent disease, which may jeopardize glycemic control (eg, infectious disease)
- Compliance to treatment is appropriate
- Compliance to diet and lifestyle is appropriate

If any of the above can reasonably explain the insufficient glycemic control, the Investigator should consider not initiating rescue medication and should undertake appropriate action, ie:

- Assess plasma glucose in fasting condition (ie, after at least 8 hours fast)
- Initiate an evaluation and treatment of intercurrent disease (to be reported in AE/concomitant medication parts of the e-CRF and the medical record)
- Stress the absolute need to be compliant with treatment

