- Organize a specific interview with the patient and a Registered Dietician or other qualified nutrition professional to reinforce the absolute need to be compliant with diet and lifestyle recommendations, and schedule a FPG/HbA1c assessment at the next visit.

If none of the above mentioned reasons can be found, or if appropriate action fails to decrease FPG/HbA1c under the threshold values, rescue medication may be introduced.

Initiation of open-label rescue medication(s) to treat hyperglycemia will be at the discretion of the Investigator and in accordance with local standard of care and prescribing practice. Except for SGLT2 inhibitors, any approved medication(s) including oral antidiabetic drugs or insulin can be prescribed to treat the hyperglycemia. The patient continues the study treatment (blinded) and stays in the study in order to collect efficacy and safety information. The planned visits and assessments should occur until the last scheduled visit. For patients with renal impairment, contraindications to antihyperglycemic drugs should be taken into consideration. If a patient requires glycemic rescue, the IMP received during the randomized, double-blind Treatment Period should continue and must remain blinded until the end of the study.

Rescue therapy is considered a NIMP. Rescue therapy is to be reported in the e-CRF. This information should include specific drug name, dose, route of administration, and frequency.

If not covered by health insurance, the cost of the rescue therapy will be reimbursed where permitted by local regulations.

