2.1.4 Safety endpoints

The safety analysis will be based on the reported adverse events (AEs), hypoglycemia, and other safety information, such as clinical laboratory data, vital signs, electrocardiogram (ECG), and physical examination, etc.

Observation period

The observation period will be divided into 4 epochs:

- The **screening** epoch is defined as the time from the signed informed consent date up to the first administration of the double-blind IMP.
- The treatment epoch is defined as the time from the first administration of double-blind IMP to the last administration of double-blind IMP. This epoch includes the 26-week double-blind core treatment period and the 53-week double-blind extension treatment period. The 26-week double-blind core treatment period is the time from the first administration of double-blind IMP to the last administration of double-blind IMP on or before Visit 9/Week 26 (or Day 182 if Visit 9/Week 26 date is missing).
- The **residual treatment** epoch is defined as the time from the last administration of double-blind IMP to the last administration of double-blind IMP + 10 days (1 day for hypoglycemia).

The treatment-emergent adverse event (TEAE) period for the 79-week double-blind entire treatment period will include both **treatment** and **residual treatment** epochs (See the TEAE period for the 26-week double-blind core treatment period in [Section 2.5.4](#)).

- The **posttreatment** epoch is defined as the period of time starting the day after the end of the treatment-emergent adverse event period up to the last protocol-planned visit or the resolution/stabilization of all serious adverse events (SAE), adverse events of special interest (AESI) and events of special interest (EOSI), whichever is later.

The on-study observation period is defined as the time from start of double-blind treatment until the end of the study (defined as the last scheduled visit for those who completed the study and the date collected on e-CRF page “Completion of End of Study/Follow-up” for those who did not complete the study).

The post-study observation period is defined as the time from the day after the end of the study until the resolution/stabilization of all SAE, AESI and EOSI if applicable.

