- Baseline BMI level ($<30, \geq 30 \text{ kg/m}^2$),
- Baseline HbA1c ($\leq 8.0\%, >8.0\%$),
- Baseline HbA1c ($\leq 8.5\%, >8.5\%$),

- Baseline mean SBP (<130 mmHg, ≥ 130 mmHg),
- Baseline eGFR (≥ 30 to <60 mL/min/1.73 m² [Moderate decrease in GFR], ≥ 60 to <90 mL/min/1.73 m² [Mild decrease in GFR], and ≥ 90 mL/min/1.73 m² [Normal]),
- Duration of diabetes (<10 , ≥ 10 years),
- Country.

The treatment effects across the subgroups defined above will be estimated for the Change from Baseline to Week 26 in HbA1c in the ITT population using the same MI method as applied to the primary analysis. The ANCOVA model will include treatment (sotagliflozin 400 mg, placebo), randomization stratum of HbA1c ($\leq 8.0\%$, $>8.0\%$), randomization stratum of SBP (<130 , ≥ 130 mmHg), subgroup factor, treatment-by-subgroup factor, and country as fixed factors and baseline HbA1c as a covariate (see sample code Part 4 of Appendix B). The adjusted estimates of treatment mean differences (sotagliflozin 400 mg versus placebo) with standard error (SE) and 95% CIs will be provided as appropriate across the subgroups. A graphical presentation of the results (ie, forest plot) will also be provided.

In the case that the subgroup factor is identical or similar to a randomization strata factor (eg, baseline HbA1c or baseline mean SBP category), only the subgroup variable (as single factor or an interaction term) will be included in the model in order to avoid the issue of collinearity in the analysis. The corresponding strata factor will not be included in the model.

Summary statistics at scheduled visits

Summary statistics (for screening value, baseline value, observed post-baseline value and its Change from Baseline) at scheduled visits will be provided for each treatment group. The summary will include the number of observations, mean, SD, standard error (SE), minimum, median, and maximum. Graphical presentations will also be used to examine trends over time using mean values (\pm SE) and mean changes from baseline (\pm SE) at each of the scheduled visits.

Similar presentations will be provided excluding measurements after rescue therapy during the entire 79-week double-blind treatment period.

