2.4.4.3 Analyses of other efficacy endpoints

The analysis of other endpoints (see [Section 2.1.3.3](#)) will be descriptive with no formal testing. Summary statistics at scheduled visits using observed values will be provided by each treatment group. Graphical presentations will also be used to illustrate trends over time.

The number (%) of patients who used rescue therapy will be summarized by treatment group during the core (see [Section 2.5.4](#)) and the entire double-blind treatment periods. A KM curve will be provided for the cumulative incidence of rescue therapy during the entire double-blind treatment period. The list of patients who used rescue therapy will also be provided (see [Section 2.5.4](#)).

UACR will be log-transformed at patient level. Summary statistics of UACR in log scale will then be calculated for each treatment group at each visit and back-transformed to provide the geometric mean and its associated percent change of UACR from baseline.

Shift tables will be provided for UACR at Week 26 and Week 79 using the pre-defined categories. That is, the number (%) of patients with progression from one category at baseline to another category at Week 26 and Week 79 will be provided by treatment group respectively. The pre-defined categories are, for urine ACR, <30 mg/g creatinine [Normal], ≥ 30 to <300 mg/g creatinine [Microalbuminuria], and ≥ 300 mg/g creatinine [Macroalbuminuria].

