2.4.5.1 Analyses of hypoglycemia

Analyses of hypoglycemia will be performed on the treatment-emergent AE periods as defined in [Section 2.1.4](#). Hypoglycemia will be classified as severe hypoglycemia, documented symptomatic hypoglycemia, asymptomatic hypoglycemia, probable symptomatic hypoglycemia or relative hypoglycemia [Section 2.1.4](#).

The number (%) of patients with any hypoglycemia, severe hypoglycemia, and documented symptomatic hypoglycemia will be summarized respectively by treatment group during the treatment-emergent AE period, as well as the incidence rate in patient years. Two types of incidence rates will be presented: the number of patients with at least 1 event per 100 patient-years (calculated as the number of patients with at least 1 event / total exposure in 100 patient-years), and the number of events per 100 patient-years (calculated as the total number of events / (total exposure in 100 patient-years)). Note: here exposure in days is duration of treatment-emergent AE period, ie, duration of IMP treatment in days +1 ([Section 2.1.4](#)).

The summary of frequency and incidence rate in patient years for severe hypoglycemia or documented symptomatic hypoglycemia will be provided as appropriate by gender (Male, Female), age group (<50, ≥ 50 to <65, ≥ 65 years) and race (White, Black or African American, Asian, Other).

A KM curve will also be provided by treatment group for the time to first severe hypoglycemia or documented symptomatic hypoglycemia during the treatment-emergent AE period for the 79-week entire treatment period only (see [Section 2.5.4](#)).

Documented symptomatic hypoglycemia maybe presented by ≤ 3.9 mmol/L (70 mg/dL) and < 3.0 mmol/L (54 mg/dL) respectively, as appropriate.

A listing of patients for all events reported on the dedicated eCRF “Hypoglycemic event information” page will be provided with flagged category (ie, severe hypoglycemia, documented symptomatic hypoglycemia, asymptomatic hypoglycemia, probable symptomatic hypoglycemia or relative hypoglycemia).

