Patients who did not experience any event during the 79-week double-blind treatment period are considered censored observations. For time to treatment discontinuation/rescue therapy, censoring date is the date of EOT. For time to severe or documented hypoglycemia, censoring date is date of EOT+1 or date of EOS, whichever is the earliest. Date of EOS will be used if date of EOT is not available. Last contact date will be used if date of EOS is not available.

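### Hypoglycaemia rates and the 79-week curve include post-rescue events and exposure, and no pre-rescue companion output by arm is planned

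*Protocol*

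**What the plan says.** **Window.** Protocol 9.2 ends the on-treatment period for hypoglycaemia one day "after the last dose of double-blind IMP, regardless of the introduction of rescue therapy". SAP 2.1.4 builds on the same dates: "The treatment epoch is defined as the time from the first administration of double-blind IMP to the last administration of double-blind IMP", followed by a one-day residual epoch for hypoglycaemia.

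**Rates and curve.** SAP 2.4.5.1 plans the number and percentage of patients with any, severe and documented symptomatic hypoglycaemia, and two incidence rates. The denominator is stated: "here exposure in days is duration of treatment-emergent AE period, ie, duration of IMP treatment in days +1". A Kaplan-Meier curve of time to first severe or documented symptomatic event is planned for the 79-week period only. SAP 2.5.4 gives its censoring rule: "For time to severe or documented hypoglycemia, censoring date is date of EOT+1 or date of EOS, whichever is the earliest". None of these is cut at rescue.

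**Rescue.** Under Protocol 8.2.2 rescued patients stay on blinded IMP, so their later time remains inside the window. SGLT2 inhibitors are barred; otherwise "any approved medication(s) including oral antidiabetic drugs or insulin can be prescribed to treat the hyperglycemia". The FPG limit is 270, then 240, then 200 mg/dL up to Week 26. The trigger that applies "after the Week 26 Visit through the end of the treatment period" is FPG above 170 mg/dL or HbA1c of at least 8.0%.

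**Companion output elsewhere.** For the HbA1c by-visit summaries, SAP 2.4.4.1 adds: "Similar presentations will be provided excluding measurements after rescue therapy during the entire 79-week double-blind treatment period". For rescue itself, SAP 2.4.4.3 gives counts by arm, a patient list and a curve: "A KM curve will be provided for the cumulative incidence of rescue therapy during the entire double-blind treatment period". Nothing links rescue to hypoglycaemia.

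**The concern.** Rescue is a post-randomisation event that can differ between arms and can itself cause hypoglycaemia. The trial is planned around a 0.6% HbA1c difference (Protocol 11.1), patients enter with HbA1c between 7% and 10% (Protocol 7.2.2), and the trigger tightens to 8.0% for the last 53 of 79 weeks. More rescue on placebo is therefore a reasonable inference, though the documents do not state it. If some rescue drugs provoke hypoglycaemia, they would add more of it to the placebo arm.

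Hypoglycaemia is a named safety endpoint, and safety over the whole 79 weeks is a stated objective. The by-arm figures that readers will use for that period would then mix the effect of sotagliflozin with the effect of rescue treatment, and no planned table separates the two. Protocol 10.4.2 acknowledges that antidiabetic co-medication complicates causality for hypoglycaemia, but its remedy is case by case and leaves these tables unchanged.

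**Working it through.** **What the documents supply.** They give no hypoglycaemia rate, rescue rate or mix of rescue agents, so there is no planned figure on this point to reproduce. The one input taken from the plan is the 0.6% HbA1c difference. The power stated with it does reproduce: 250 per arm and SD 1.2% give 0.9999, against at least 99%. Everything else below is an assumption.

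**Step 1: share meeting the post-Week-26 trigger.** Take Week 26 HbA1c as normal, with placebo mean 7.8, 8.0 or 8.2, SD 0.8, 1.0 or 1.2, and sotagliflozin 0.6 lower. The share at or above 8.0% is p = 0.401 to 0.599 on placebo and t = 0.159 to 0.369 on sotagliflozin (nine pairs, kept paired).

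**Step 2: planned event-rate ratio.** Assume rates without rescue of 0.10 (sotagliflozin) and 0.05 (placebo) events per patient-year, a true ratio of 2.0. Then

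planned ratio = (0.10 + t·c·a·r·w·m) / (0.05 + p·c·a·r·w)

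- c: share of trigger-positive patients actually rescued (1 or 0.5)
- a: share of those given an agent that causes hypoglycaemia (0.3, 0.4, 0.5)
- r: events per patient-year added by that agent (0.3, 0.45, 0.6)
- w: share of the 79 weeks spent after rescue (53/79 or 40/79)
- m: factor by which sotagliflozin multiplies the added rate (1 = same absolute addition in both arms)

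One point in full: mean 8.0, SD 1.0, c = 1, a = 0.4, r = 0.45, w = 53/79 = 0.671, m = 1. Placebo gains 0.500 × 0.4 × 0.45 × 0.671 = 0.0604 and sotagliflozin 0.274 × 0.4 × 0.45 × 0.671 = 0.0331. The ratio is 0.1331 / 0.1104 = 1.21. With m = 2 it is 0.1662 / 0.1104 = 1.51.

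Over all 9 × 2 × 3 × 3 × 2 = 324 points:

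| Assumption on added rate | Range | Median | Points below 1 |
|---|---|---|---|
| Equal in both arms (m = 1) | 0.95–1.77 | 1.40 | 2 |
| m = 1.25 | minimum 1.04 | | 0 |
| m = 2 | 1.25–1.86 | | 0 |

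With m = 1 the range is 0.95–1.60 if all trigger-positive patients are rescued and 1.19–1.77 if half are. If few rescued patients get such an agent (a = 0.05 to 0.2, r = 0.1 to 0.6), it is 1.27–1.98. If r = 0 it stays 2.00.

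**Step 3: counts of patients.** Repeated events in one patient count once in n (%). Take Poisson events over 79 weeks (T about 1.51 years). With f the trigger share (p or t) and b the background rate, the share with an event is (1 − fca)(1 − exp(−bT)) + fca(1 − exp(−(b + rw)T)). On the same grid with m = 1, the n (%) ratio is 1.01 to 1.73, against 1.93 without rescue. The Kaplan-Meier curve was not modelled.

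**Step 4: a second, simpler model.** Pre-rescue rates of 3 and 6 per 100 patient-years, and one total post-rescue rate common to both arms, so the sotagliflozin excess vanishes after rescue. With 10%/5% of exposure after rescue (placebo/sotagliflozin), the ratio is 1.82 to 1.26 as the post-rescue rate goes from 6 to 30. With 20%/8% it is 1.67 to 0.94, and with 30%/10% it is 1.54 to 0.76. It reaches 1 only at post-rescue rates of 60, 26 and 16.5, which are 20, 8.7 and 5.5 times the placebo pre-rescue rate. If sotagliflozin also doubles the post-rescue rate, the range is 1.03 to 1.91.

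**Step 5: what ending at rescue costs.** Exposure kept is 1 − p·c·w = 0.60 to 0.90 on placebo and 1 − t·c·w = 0.75 to 0.96 on sotagliflozin. If rescued patients have k times the underlying rate of others, with arm averages held at 0.10 and 0.05, the pre-rescue ratio is 1.85–1.96 for k = 0.5 and 2.01–2.10 for k = 1.5.

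**The case against.** The planned summary is stated openly and answers a proper question: what happens under assignment to each arm, rescue included, while on IMP. No test or decision rule depends on it, since safety is descriptive (SAP 2.4.5). Protocol 4.2 reports no significant adverse-event imbalances in completed studies, background therapy is metformin alone, and a two-fold excess is an illustration. All of that stands. It makes this a missing companion output rather than an error.

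Existing outputs also help. Counts and rates are given separately for the 26-week core period, when FPG limits are looser and HbA1c is not a trigger. There are also rescue summaries by arm, a rescued-patient list, a listing of every hypoglycaemia event, and in Protocol 11.4.3.2 an assessment of pattern over time. These cover the gap only in part. The core tables still contain post-rescue events and say nothing about Weeks 27 to 79. The listings would allow a pre-rescue analysis, but only one chosen after the results are known.

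A reader might go further and infer that a real excess would be masked. The documents do not support that. In the main grid the two points below 1 need every trigger-positive patient rescued at exactly Week 26, half of them on an agent adding 0.6 events per patient-year, and no extra sotagliflozin effect on that addition. Protocol 8.2.2 requires a confirmatory test and a search for other explanations, and leaves rescue to the Investigator's discretion. The sub-1 results in the simpler model need a post-rescue rate several times background and no drug effect after rescue.

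Finally, censoring at rescue is itself informative. That also stands, and it limits the role of the added output.

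**Conclusion.** The concern holds as a minor one. No planned hypoglycaemia output separates time before rescue from time after it. If rescue is commoner on placebo and rescue drugs add hypoglycaemia, the 79-week comparison is pulled toward no sotagliflozin excess. Both conditions are assumptions. The documents support the first by inference and permit the second by allowing insulin.

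The size cannot be derived from the documents. On the assumptions shown, a true event-rate ratio of 2.0 would typically read about 1.4. The effect is weaker if sotagliflozin also raises the added rate, if few rescued patients get an agent that causes hypoglycaemia, or if the measure is n (%). Dilution is the supportable claim. Complete masking is not a realistic expectation, and nothing here shows that an excess exists.

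**What to change.** In SAP 2.4.5.1, keep the planned all-data tables as the main summary and add:

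- n (%) and both incidence rates for any, severe and documented symptomatic hypoglycaemia, for the core and 79-week periods, with events and exposure ending at the first rescue dose;
- a 79-week Kaplan-Meier curve for the already planned time to first event, censored at rescue;
- a post-rescue flag in the hypoglycaemia event listing.

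SAP 2.5.3 does not impute medication dates. For this supplementary output only, state a rule for partial rescue start dates, for example the earliest date consistent with the record, and list the affected patients. Early dating can drop genuine pre-rescue events, so the list matters.

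The cost is one SAP paragraph, a few repeat tables and one curve. No new data are needed: rescue is identified on the e-CRF medication page (SAP 2.1.3), hypoglycaemia onset date and time are collected (Protocol 10.6.1), and time to rescue is already defined (SAP 2.5.4). The downside is informative censoring of uncertain direction. In the illustration the pre-rescue ratio runs from 1.85 to 2.10 against a true 2.0 when rescued patients have 0.5 to 1.5 times the underlying risk of others. The SAP should therefore say that these outputs support the planned summary and do not replace it.
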